Participants will be recruited from community physiotherapy clinics in BC within Fraser Health. Community health centres within the metropolitan areas of Delta, Surrey, Burnaby, New Westminster, Langley, Coquitlam, Maple Ridge, Chilliwack, Mission, and Abbotsford, on social networking websites (Facebook, Twitter, Kajiji, Craigslist), and the Arthritis Research Canada website. Participants will also be recruited from Arthritis Consumer Experts' (ACE) JointHealth e-blast, ARC Arthritis Patient Advisory Board, consumer collaborators' group newsletters, websites, and social media (e.g. CARP, The Arthritis Society), and VCHRI weekly e-update which is distributed to staff, researchers, faculty, and affiliates of VCHRI. To ensure the research is completed in the timely manner, the RCT recruitment will begin during usability testing. Eligible and consenting individuals will be re-consented when the RCT enrolment is ready.

Study Procedure (Figure 3): Interested individuals will contact the research assistant who will screen for eligibility and obtain informed consent. After completing the baseline measures, they will be randomly assigned to the Immediate Intervention Group or the Delayed Intervention Group (i.e. control) in 1:1 allocation ratio. Randomization will be performed using computer-generated random numbers in variable block sizes, which are necessary to ensure adequate allocation concealment.

The Immediate Intervention Group will attend a 1.5-hour group education session (3-6 participants), where they will receive standardized education by a PT from Fraser Health Authority or Vancouver Coastal Health. The session will address physical activity and the detrimental effect of sedentary behaviour in people with OA. Ways to increase enjoyment while exercising will be highlighted, such as exercising outdoors and with music. Research staff will be present to set up participants' Fitbit and FitViz app. At the end of the session, the PT will help participants set activity goals and provide personalized activity options.

In Months 1-2, participants will use the Fitbit/FitViz app. Information about their physical activity and sedentary behaviours will be captured by the Fitbit and wirelessly synchronized with the FitViz app's

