Activity Tracker function. The app will display personalized activity summaries, which will be shared with the study PT. The PT will review the progress with participants via four biweekly phone calls and progressively modify their activities. Participants may also contact the PT via email at any time if they have questions. In Months 3-9, participants will continue using the Fitbit/FitViz app and have access to the PT via email, but no biweekly phone calls. The Delayed Intervention Group will receive the full intervention three months later. Both groups will receive a monthly study newsletter during the 9-month period.

Follow-up assessments will be performed at the end of Months 3, 6 and 9. To better understand the reasons people do or do not adopt and maintain recommended levels of physical activity, all participants will be interviewed for one hour by phone after the intervention by a PhD medical sociology trainee. Interviews will focus on 1) goals set, strategies used, barriers/facilitators to being physically active, 2) their experience with the intervention, 3) the nature of activities they engage in, and 4) their experience of being a research participant. These data will enrich the RCT data, and inform the design of the future implementation strategy.

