**Power Calculation:** Our collaboration with PABC, Fraser Health, and patient groups will allow the study to recruit 60 eligible participants within 6 months. For a proof-of-concept study, it is reasonable to expect moderately large difference between groups after the physical activity intervention. In one of our pilot studies involving 27 patients with RA, [name] et al. found an average of 71.8 minutes (SD=96.2) of activities at 3 METs bouted at 10-minute intervals (unpublished data). Assuming an attrition rate of approximately 15%, we anticipate 50 of the 60 participants will complete the study. With a sample size of 50 and  $\alpha$ -level of 0.05, we will have 96.3% power to detect a between-group difference of at least 10 minutes, or 13.9% in the primary outcome measure after the intervention (Appendix C).

**Data Management:** Prior to use, the SenseWear unit will be configured using the participant's handedness, smoking status, age, sex, height and weight and set to collect data in one-minute intervals. All data will be downloaded and processed using the SenseWear Professional™ software (Version 8.1), and stored at the secured server at ARC, which backs up the data every 24 hours. The processed data will then be exported for further processing and data analysis using a customized data analysis protocol developed by [name] using MATLAB® software. Self-reported outcome measures will be administered using the online survey system hosted by ARC. This is a fully encrypted, secure website with 128-bit SSL encryption, which is also used by many major banks. To minimize human error, skip logics for questions and the available range for each variable will be programmed in the online questionnaire. Databases will be created in the Microsoft Excel format, which can be easily converted into SAS, SPSS, and other statistical packages for statistical analysis. We will use multiple imputations to investigate the impact of missing data in the study, although every effort will be used to minimize the amount of missing data.

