**Data Analysis:** Because the aim of a proof-of-concept study is to demonstrate evidence of efficacy, an intention-to-treat analysis will be performed. The main analysis will include the bouted mean moderate/vigorous activity minutes (primary outcome measure), bouted mean sedentary minutes, the KOOS and the Partners in Health Scale. For the main comparison, we will use analysis of covariance (ANCOVA) to compare between the Immediate Intervention Group and Delayed Intervention Group at 3 months, using the baseline measure as a covariate. In addition, ANCOVA will be used to assess the difference between the Intervention Group at 3 months and the Control Group at 6 months, with the baseline measure as a covariate. We anticipate that the two groups should be similar if the delay of 3 months in the Delayed Intervention Group does not influence the effect of the intervention. We will also use repeated measure ANOVA to assess the within group differences over the four assessment periods. No adjustment will be made for multiple comparisons because Type II error is a greater concern than Type I error in proof-of-concept studies. Descriptive analysis will be used to summarize participant characteristics and comorbid conditions.

The literature suggests that physical activity and chronic disease self-management experiences are different for men and women. Although this project is not powered to examine the effect in outcomes for men and women separately, exploratory analysis will be done to assess trends in each group. The results will provide information for a sample size calculation in future studies of online physical activity interventions.

We will also examine the mechanism of the intervention on physical activity participation by conducting mediation analysis using the bootstrapped sampling distribution model by Preacher & Hayes. Changes in Theory of Planned Behaviour variables over the intervention period (i.e., between baseline and 3 months) will be examined as potential mediators on physical activity behaviour after the 3-month intervention.

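### Does teaching the Immediate arm in shared sessions of 3-6 make the Month-3 ANCOVA too precise?

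*Combined protocol and SAP*

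**What the plan says.** All of this is in Section 4.3. After baseline, "they will be randomly assigned to the Immediate Intervention Group or the Delayed Intervention Group (i.e. control) in 1:1 allocation ratio", so the unit of randomisation is the person. Delivery is then grouped: "The Immediate Intervention Group will attend a 1.5-hour group education session (3-6 participants", with "standardized education by a PT from Fraser Health Authority or Vancouver Coastal Health". At the end of the session the physiotherapist helps each person set goals and offers personalised options. Four individual phone calls follow in Months 1-2.

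For the other arm, "The Delayed Intervention Group will receive the full intervention three months later". It has therefore had no session by Month 3. Its session size is not stated, although the eligibility criteria require every participant to be able to attend a group session.

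For the main comparison, "we will use analysis of covariance (ANCOVA) to compare between the Immediate Intervention Group and Delayed Intervention Group at 3 months", with the baseline measure as the only named covariate. In a second comparison, "ANCOVA will be used to assess the difference between the Intervention Group at 3 months and the Control Group at 6 months", and the plan expects the two groups to be similar there. Neither the power nor the analysis paragraph mentions a session or physiotherapist effect, an ICC or a design effect. The analysis paragraph also declines multiplicity adjustment, on the ground that Type II error matters more than Type I in a proof-of-concept study.

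**The concern.** At Month 3 one arm has been taught in groups and the other has not, which makes the design partially nested. People who shared a session may do better or worse together because of that physiotherapist, that group's dynamics or that day's teaching. If so, each person in the Immediate arm carries less than one person's worth of independent information. An ANCOVA that ignores this reports a standard error that is too small, a confidence interval that is too narrow and a test that can exceed its nominal 5%.

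The Immediate Month-3 versus Delayed Month-6 comparison looks more exposed, because both arms would by then have been taught in groups. A false positive there would be read as an effect of the three-month delay. A statistician used to group-delivered interventions would look for a session term and find none.

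**Working it through.** The plan has no clustering figure to reproduce. Its 96.3% power does not enter here. That figure does not follow from the printed inputs (25 per arm, 10 minutes and SD 96.2 give 5.6%), but that is a separate question, and the appendix holding the calculation is not in the supplied text.

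**Inputs**
- Session size m = 3 to 6 (Study Procedure).
- Retention 50/60 (Power Calculation: "we anticipate 50 of the 60 participants will complete the study").
- Two-sided alpha 0.05. The level is stated; two-sided is assumed.
- ICC: not documented. Assumed range 0 to 0.10.
- Sessions per arm: 30 randomised / 6 = 5, up to 30 / 3 = 10.

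**Formulas**
- Random loss leaves unequal sessions, so the expected number of analysed session-mates is (50/60)(m − 1). The design effect in a grouped arm is DE = 1 + (50/60)(m − 1) × ICC.
- Month 3, one arm grouped: variance ratio f = (DE + 1)/2. Both arms grouped: f = DE.
- Understatement of the standard error = 1 − 1/√f. Type I error = 2(1 − Φ(1.96/√f)).

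**Worked case, m = 6, ICC 0.05, Month 3.** (50/60) × 5 = 4.167; DE = 1 + 4.167 × 0.05 = 1.208; f = 1.104; √f = 1.051. The standard error is 4.8% too small. 1.96/1.051 = 1.865, so type I error is 6.2%.

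| ICC | Month 3, m = 3 | Month 3, m = 6 | Both arms grouped, m = 3 | Both arms grouped, m = 6 |
|---|---|---|---|---|
| 0 | 0% (5.0%) | 0% (5.0%) | 0% (5.0%) | 0% (5.0%) |
| 0.01 | 0.4% (5.1%) | 1.0% (5.2%) | 0.8% (5.2%) | 2.0% (5.5%) |
| 0.05 | 2.0% (5.5%) | 4.8% (6.2%) | 3.9% (6.0%) | 9.0% (7.5%) |
| 0.10 | 3.9% (6.0%) | 9.0% (7.5%) | 7.4% (7.0%) | 16.0% (10.0%) |

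Entries are the understatement of the standard error, with type I error in brackets. Simulated ANCOVAs (40,000 runs, 30 per arm, random 50/60 retention, assumed baseline correlation 0.5) agree. With five sessions of 6, Month-3 type I error at ICC 0, 0.01, 0.05 and 0.10 was 5.1, 5.2, 6.4 and 7.5%.

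**Missing data.** With no loss at all, sessions of 6 at ICC 0.10 give DE = 1.5 and f = 1.25, so the Month-3 standard error is 10.6% too small. With both arms grouped, f = 1.5 gives 18.4%. Multiple imputation does not bring those figures back: values imputed without a session term carry no session correlation. In a simulation of five sessions of 6, the Month-3 understatement at ICC 0.05 was 4.9% imputed, 5.4% in completers and 6.3% with nothing missing. At ICC 0.10 it was 8.8, 9.7 and 11.4%. The plan's stated use of imputation is a check in any case: "We will use multiple imputations to investigate the impact of missing data in the study".

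**When type I error is affected.** Sessions are formed after individual randomisation. If the intervention affects no one, the ANCOVA keeps its 5% level however people are sorted: with a within-session ICC of about 0.05-0.10 from sorting alone, it simulated at 4.8-5.2%. Inflation needs session effects that vary around an average of exactly zero.

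**What a nested model would return.** The candidate is a baseline-adjusted mixed model with a random session effect in the Immediate arm and Satterthwaite degrees of freedom.
- At ICC 0.05 it estimated zero session variance in about 48% of simulated trials, so it then repeats the primary result.
- At ICC 0 its interval was on average 5-11% wider than the ANCOVA's. At an effect giving the ANCOVA about 80% power, its power fell from 80.1 to 77.1% (ten sessions of 3), 80.4 to 74.5% (six of 5) and 79.6 to 72.3% (five of 6).
- With sorting only, its type I error fell to 2.8-4.3%.
- An ICC estimate of 0.05 from five sessions of 5 has a 95% interval of about −0.15 to 0.66.

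**The case for a change.** The best case for acting is that it costs almost nothing. Session and physiotherapist identifiers are two variables, and if nobody records them no one can examine clustering later. The same physiotherapist may also make the follow-up calls, a second source of correlation lasting through much of the period before Month 3. The trial is meant to inform later studies, for which even an imprecise ICC might help. The Month-3 versus Month-6 comparison is the more sensitive one, and with no multiplicity adjustment readers will lean on interval widths.

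Much of this stands. The independence assumption is not examined, the direction of the bias is right, and the group-session eligibility criterion supports grouped delivery in both arms. Keeping the identifiers is good practice, but it is a study-records detail that a competent team handles without a plan amendment.

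The case for adding a model is weaker. Used only as a sensitivity check, it could not overturn the primary result. A wider interval could come from clustering, sorting or the degrees-of-freedom penalty, and the trial could not tell these apart. An ICC with an interval that wide would give a later trial little to plan on. The number of physiotherapists is not stated; with one or two, their effect could not be reliably estimated.

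**Conclusion.** The point is technically correct but too small and uncertain to change the plan. At an assumed ICC of 0.01-0.05 and 50/60 retention, the Month-3 standard error is understated by about 0.4-5% and type I error is about 5.1-6.2%. At ICC 0.10 the upper figures are about 9% and 7.5%, or nearer 10% for the standard error in simulation. If both arms are grouped, the Month-3 versus Month-6 comparison could reach 16% and 10% at ICC 0.10 with sessions of 6.

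These figures rest on an assumed ICC. The documents suggest a low one: a single standardised session, then individual goals, app summaries and calls. An ICC well above 0.10 would weaken this conclusion, but nothing in the text points to one.

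Keeping the plain ANCOVA is a fair trade-off. The alternative gives up power the plan has said it values, in return for a variance component that 5-10 sessions per arm cannot estimate. The unstated Delayed-arm session size and the unmentioned identifiers are details analysts can settle sensibly, with possible clustering noted as a limitation when results are reported.

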**Outcome Measures:** Our **primary outcome measure** will be time spent in moderate/vigorous physical activity. In addition, we will record the time spent in sedentary behaviours. Participants will wear a SenseWear Mini accelerometer for 7 days at baseline, and Months 3, 6 and 9. SenseWear is a multi-sensor monitor that is worn on the upper arm over the triceps. It integrates tri-axial accelerometer data, physiological sensor data and personal demographic information to provide estimates of steps, energy expenditure and METs. Almeida et al. determined that a minimum of 4 days of wear is required to reliably assess energy expenditure from different levels of physical activity in people with RA (intraclass correlation coefficient - ICC > .80). Tierney et al. showed in 2013 that SenseWear was a valid tool for estimating energy expenditure during activities of daily living in this population (ICC = 0.72). Further, a strong relationship was found between SenseWear and indirect calorimetry measures of energy expenditure for activities of daily living (Pearson's  $r = 0.85$ ). SenseWear can be worn 24 hours a day. Hence, it can capture a full picture of physical activity and sleep pattern, as well as the off-body time throughout the day.

An important feature of the SenseWear Mini is its ability to differentiate between sedentary and non-sedentary/light physical activities, making it an ideal instrument to assess both active and sedentary behaviours. We will calculate the **average daily moderate/vigorous activity accumulated in bouts per day**. A bout is defined as 10 or more consecutive minutes at the level of  $\geq 3$  METs (i.e., the lower bound of moderate/vigorous activity), with allowance for interruption of up to two minutes below the threshold. For sedentary behaviours, we will calculate the average daily time spent with an energy expenditure of  $< 1.6$  METs, occurring in bouts of 20 minutes or more during waking hours.

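### The stated 96.3% power for a 10-minute difference does not follow from the plan's SD of 96.2 minutes and 50 completers; those inputs give about 6.5% to 13%

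*Combined protocol and SAP*

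**What the plan says.** All the inputs are in Section 4.3 (Aim 3).

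- **Power Calculation, expected effect:** "it is reasonable to expect moderately large difference between groups after the physical activity intervention".
- **Power Calculation, pilot data:** "In one of our pilot studies involving 27 patients with RA", the team "found an average of 71.8 minutes (SD=96.2) of activities at 3 METs bouted at 10-minute intervals". This is the only mean and SD given for the outcome. It has no per-day or per-week label.
- **Power Calculation, numbers:** "we anticipate 50 of the 60 participants will complete the study".
- **Power Calculation, conclusion:** "we will have 96.3% power to detect a between-group difference of at least 10 minutes, or 13.9% in the primary outcome measure", at alpha 0.05. Sidedness is not stated. The calculation is referred to Appendix C, which is not in the text available for review; that is not a criticism of the plan.
- **Study Procedure:** 1:1 randomisation, so 25 completers per arm.
- **Outcome Measures:** the primary outcome is the "average daily moderate/vigorous activity accumulated in bouts per day", that is, minutes per day.
- **Data Analysis:** the main comparison is a two-group ANCOVA at 3 months with baseline as covariate. No baseline to Month 3 correlation is given.

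**The concern.** A 10-minute difference is about one tenth of the stated SD. That is a very small standardised effect, not a moderately large one, and 25 people per arm cannot detect it with high probability. The claimed power and the SD printed just before it are incompatible.

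Two things are at stake. First, a reader who believes the 96.3% would take a non-significant result as good evidence against a 10-minute effect, when on the stated inputs it would say almost nothing about one. Second, the Data Analysis paragraph declines to adjust for multiple comparisons because Type II error is the greater worry. The stated power implies a Type II error of 3.7%; the stated inputs imply about 87% to 93%.

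**Working it through.** **Inputs.** Difference 10 minutes, pilot mean 71.8, SD 96.2, alpha 0.05 and 50 completers (Power Calculation); 1:1 allocation (Study Procedure); ANCOVA on baseline (Data Analysis). Two assumptions are mine: a two-sided test as base case, and a range for the baseline to Month 3 correlation r.

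**Step 1. Units.** 10/71.8 = 0.1393, which reproduces the stated 13.9%. The 10 minutes and the 71.8 (SD 96.2) are therefore on one scale. The standardised difference is d = 10/96.2 = 0.104, whether that scale is daily or weekly.

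**Step 2. Attempt to reproduce 96.3%.** For a two-sample t-test with n = 25 per arm, the noncentrality is d × √(n/2) = 0.104 × √12.5 = 0.37 on 48 degrees of freedom. Two-sided power is **6.5%**. The stated figure is not reproduced.

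**Step 3. Credit for ANCOVA.** Baseline adjustment reduces the SD to 96.2 × √(1 − r²):

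| r (assumed) | Residual SD | Two-sided power, 25 per arm | One-sided power, 25 per arm | Two-sided power, 50 per arm |
|---|---|---|---|---|
| 0 | 96.2 | 6.5% | 10.0% | 8.1% |
| 0.5 | 83.3 | 7.0% | 11.0% | 9.1% |
| 0.7 | 68.7 | 8.0% | 12.8% | 11.1% |
| 0.9 | 41.9 | 13.1% | 20.8% | 21.9% |
| 0.95 | 30.0 | 21.1% | 31.4% | 37.8% |

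Analysing all 60 randomised (30 per arm) gives 6.8% at r = 0 and 14.9% at r = 0.9. A one-sample or paired test with n = 50 and SD 96.2 gives 11.1%.

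**Step 4. What 96.3% would need.** With 25 per arm, 96.3% power requires d = 1.082. For 10 minutes that is a residual SD of 10/1.082 = 9.2 minutes, so r = √(1 − (9.245/96.2)²) = 0.995.

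**Step 5. What the design can detect.** For 80% power, d = 0.809:

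- r = 0: 0.809 × 96.2 = 78 minutes
- r = 0.5: 67 minutes
- r = 0.7: 56 minutes (77% of the pilot mean)
- r = 0.9: 34 minutes (47% of the pilot mean)

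**Step 6. Possible origin (inference only).** The pilot's standard error is 96.2/√27 = 18.51. Entering 18.51 as the SD in a two-sided one-sample t-test with n = 50 gives 96.28%, which matches the stated figure. That recipe treats a standard error as an SD and the two arms as one group; with 18.51 and 25 per arm, power is 46%. A decimal slip to SD 9.62 gives 95.0% and fits less well. The finding does not depend on either explanation.

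**The case against.** The strongest reply concerns the missing time base. The primary outcome is in minutes per day. If 96.2 is a weekly SD, the daily SD is 96.2/7 = 13.7, and a difference of 10 minutes *per day* would have 71% power at r = 0, 83% at r = 0.5 and 94% at r = 0.7. A daily reading of the pilot mean is also not obviously right: 71.8 × 7 = 503 minutes per week, while Section 2.0 cites a review in which only 13% of people with OA reached 150 minutes per week in bouts. That comparison is only suggestive, because the pilot patients had RA and an SD larger than the mean points to a skewed distribution.

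This does not rescue the printed sentence. The 13.9% ties the 10 minutes to the 71.8. If both are weekly, the target is 10/7 = 1.4 minutes per day and power is unchanged at 6.5% to 13%. If the 10 is daily and the 71.8 weekly, the relative difference would be 10/10.26, about 97%, not 13.9%.

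Part of the objection does stand. The true power for 10 minutes per day depends on the real daily SD in knee OA, which the plan does not establish. The low figures are what the stated inputs imply; they are not a measured property of the trial. Appendix C might use another SD, but then the paragraph has to state it.

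It can also be said that 60 participants reflects what can be recruited for a proof-of-concept study. That is a fair reason for the sample size, but it does not support a precise and incorrect power figure.

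**Conclusion.** The concern holds. The 96.3% is wrong as written: the plan's own mean, SD, completers, alpha and allocation give 6.5% two-sided power unadjusted and 7.0% to 13.1% with ANCOVA for correlations of 0.5 to 0.9. The shortfall is roughly 83 to 90 percentage points. Neither one-sided testing (10% to 21%) nor 50 per arm (8% to 22%), each over correlations of 0 to 0.9, comes near the claim.

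This rests on the SD of 96.2 applying on the same scale as the 10 minutes, which the 13.9% confirms, and on correlations that are assumed because the plan gives none. The SD comes from 27 people with RA and may differ in knee OA, but the residual SD would have to be about a tenth of the stated SD to justify the figure.

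**What to change.** Rewrite the power paragraph and Appendix C so that the figure follows from stated inputs:

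1. Give the SD actually used, its source and its time base, and express the target difference and SD in minutes per day, as for the primary outcome.
2. State the sidedness of alpha, the number per arm and the assumed baseline to Month 3 correlation.
3. Replace the 96.3%. If 96.2 stands as the SD on the outcome scale, suitable wording is: *With 25 completers per arm, SD 96.2 minutes, two-sided alpha 0.05 and an assumed baseline to Month 3 correlation of 0.7, ANCOVA has 80% power for a difference of about 56 minutes; power for a 10-minute difference is about 8%.* If the SD proves to be weekly or otherwise different, recompute and also correct the 13.9%.
4. Remove or reword the expectation of a moderately large difference so that it agrees with the effect size used.
5. Preferably, add that the estimate will be reported with its 95% confidence interval and that a non-significant result will not be read as absence of effect.

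The cost is a rewritten paragraph and appendix, and a power statement that will be much less favourable if 96.2 stands. No extra participants or procedures are needed; the sample size can rest on feasibility and the proof-of-concept aim.

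### Does the primary ANCOVA on raw bouted minutes need a pre-specified skew analysis or influence check?

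*Combined protocol and SAP*

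**What the plan says.** Section 4.3, Outcome Measures, defines the primary variable as "average daily moderate/vigorous activity accumulated in bouts per day". Under Data Analysis the plan says "we will use analysis of covariance (ANCOVA) to compare between the Immediate Intervention Group and Delayed Intervention Group at 3 months", adjusted for baseline and analysed by intention to treat. No transformation is stated, so the natural reading is raw minutes.

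Two nearby methods serve other purposes: multiple imputation is for missing data, and the bootstrap is for the mediation analysis. Nothing is said about outliers, influence or an alternative scale for the primary comparison.

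The only planning data are in the Power Calculation, which "found an average of 71.8 minutes (SD=96.2) of activities at 3 METs bouted at 10-minute intervals (unpublished data". Their source is described as "In one of our pilot studies involving 27 patients with RA". The target there is "a between-group difference of at least 10 minutes, or 13.9% in the primary outcome measure", a difference in mean minutes.

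**The concern.** Minutes cannot be negative, and here the SD exceeds the mean. Many low values with a few very high ones are likely, and section 2.0 points the same way: over 90% of people with knee OA in one cited study fell short of activity guidelines. Counting only bouts of 10 minutes or more also makes zeros plausible.

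With about 50 completers, one very active person could shift the adjusted difference by as much as the 10 minutes being sought, and could inflate the residual SD. If no check is fixed in advance, a reader may be unable to tell whether the result rests on that person, and a check chosen after the data are seen could be selective.

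**Working it through.** **Inputs.** From section 4.3: mean 71.8, SD 96.2, difference 10 minutes, alpha 0.05, 50 completers, 1:1 allocation (25 per arm). Assumed, because the documents give neither: the shape of the distribution and the correlation r between baseline and month 3.

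**1. The plan's own figures.** The percentage reproduces: 10/71.8 = 13.9%. The power does not. The SE of an unadjusted difference is 96.2 × √(2/25) = 27.2 minutes, 10/27.2 = 0.367, and two-sided power is Φ(0.367 − 1.96) = 5.6%. ANCOVA with r = 0.9 gives 13.2%. Reaching 96.3% needs a residual SD of about 9.4 (two-sided). Reading 96.2 as a variance gives SD √96.2 = 9.8 and power of 95.0% two-sided or 97.5% one-sided. Appendix C is not in the supplied text, so the source of 96.3% cannot be checked.

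**2. Is skew implied?** Taking 96.2 as the SD:
- CV = 96.2/71.8 = 1.34, whether the figures are per day or per week.
- A normal shape would put Φ(−71.8/96.2) = 22.8% of values below zero.
- Any non-negative variable with these moments has skewness of at least CV − 1/CV = 1.340 − 0.746 = 0.59.
- Gamma: 2 × CV = 2.7. Lognormal: 3 × CV + CV³ = 4.02 + 2.41 = 6.4.

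Right skew follows from the figures. That it is strong depends on the assumed shape.

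**3. Does the planned test survive it?** Simulated ANCOVA on raw minutes, 25 per arm, 20,000 trials per row, two-sided 5%. The shift is the largest change in the adjusted difference from removing one participant. An added constant effect does not alter it.

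| Shape | Latent r | Type I error | Median SE | Median largest shift | Shift/SE | Shift above 10 min |
|---|---|---|---|---|---|---|
| Normal | 0.6 | 5.0% | 21.8 | 8.1 | 0.37 | 15% |
| Normal | 0.8 | 5.0% | 16.4 | 6.1 | 0.37 | 1% |
| Gamma | 0.6 | 4.7% | 21.8 | 11.7 | 0.54 | 67% |
| Gamma | 0.8 | 4.5% | 16.8 | 9.0 | 0.54 | 39% |
| Lognormal | 0.6 | 4.1% | 18.9 | 11.3 | 0.60 | 60% |
| Lognormal | 0.8 | 3.9% | 14.8 | 8.7 | 0.59 | 40% |

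The test does not exceed its nominal level.

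**4. How large is the influence?** Ten minutes is a small yardstick here: 10/21.8 = 0.46 SE. Under skew, the 95% interval already spans roughly ±2.01 × 14.8 = ±30 to ±2.01 × 21.8 = ±44 minutes. In further simulations with r from 0.5 to 0.8, the largest shift exceeded one SE in only 1% to 6% of skewed trials. With r of 0.5 and 0.7 and a true +10 minutes, one removal could reverse the sign in 32% to 35% of skewed trials, against 24% to 25% with normal data. It changed significance in 15% to 18%, against 11% to 12%. Most of this instability would be present with normal data of the same SD.

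**5. Would another scale do better?** Rejection rates over lognormal, gamma and 20%-zeros shapes, r of 0.5 and 0.7, 10,000 trials per setting:

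| Truth | Raw | Square root |
|---|---|---|
| No effect | 4.0–4.9% | 4.6–5.0% |
| +10 minutes for everyone | 7–9% | 13–22% |
| ×1.139 | 6–7% | 6–8% |
| Equal means, spread cut by 30% | 5–6% | 11–23% |

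In the last row rank ANCOVA rejects in 16% to 37%. The square root gains clearly for a constant shift, hardly at all for a proportional effect of the planned size, and it reacts to changes of shape when mean minutes are equal.

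**6. If 96.2 is a variance** and the data are near normal, the largest shift (median 8.7 minutes at r = 0.5, normal data) scales to 8.7 × 9.8/96.2 = 0.9 minutes, and nothing is left of the concern.

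**The case for a change.** The best case for a change is that it costs two or three sentences, leaves the primary test alone and prevents selective choice of checks later. Under the printed SD and r of 0.5 to 0.7, removing one participant moves the estimate by 10 minutes or more in 50% to 73% of skewed trials, against 6% to 25% with normal data. It also lowers the residual variance by a median of 27% to 35%, against 11%. The plan adds that "The results will provide information for a sample size calculation in future studies of online physical activity interventions", and a future sample size scales with that variance.

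Part of this stands: the plan is silent, skew does raise influence, and a leave-one-out range printed beside the confidence interval would be informative. The rest carries less weight.

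- The 50% to 73% depends on r. At r = 0.8 the share is 36% to 40%.
- The sentence on future sample size follows the exploratory analysis by sex. Nothing says that the residual SD of the primary model will be used.
- A leave-one-out range of the SD could mislead. In skewed simulations the full-sample residual variance was already below the true value in 60% to 79% of trials, and the lowest leave-one-out value was below it in 88% to 97%. Planning on the low end would underpower the next trial. A confidence interval for the SD is the ordinary tool.
- A square-root analysis does not show whether one participant drives the result. At +10 minutes it alone is significant in 6% to 14% of trials, which adds a discordant p-value without resolving anything. Log, rank and robust methods are equally defensible, so the choice is a preference.

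**Conclusion.** No change is called for. The plan leaves out a routine diagnostic that an analyst would supply when reporting; the primary analysis is sound as written. Raw-scale ANCOVA holds its level (3.9% to 4.7% under gamma or lognormal skew, 25 per arm) and estimates the quantity that the plan targets. A supportive analysis that could not alter the conclusion adds reporting, not correctness.

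The extra influence due to skew is modest: a median largest shift of 0.54 to 0.60 SE, against 0.37 SE for normal data with the same SD. These figures assume that the mean and SD from 27 RA patients carry over to knee OA, that 96.2 is an SD, that the shape is gamma or lognormal, and that latent r is 0.6 or 0.8. The conflict between SD 96.2 and 96.3% power is a separate and larger question. An influence check would not settle it, and if 96.2 is a variance the present point has no practical force.
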